3.2 Measures Taken to Avoid and Minimize Bias

Several measures will be taken to avoid and minimize bias in this clinical investigation, including randomization, blinding, having an independent Clinical Events Committee (CEC) for key adverse event adjudication as well as having an independent echocardiographic core laboratory and an independent angiographic core laboratory for imaging data analyses. Blinding to minimize bias will be discussed in **Section 3.2.1** below. Details on randomization, CEC, and core laboratories can be found in **Sections 6.2, 10.8.3, and 6.10**, respectively.

3.2.1 Blinding

This is an open-label clinical investigation. The subjects and the investigators will not be blinded to the treatment assignment. Nevertheless, measures of blinding will be taken to minimize bias and will be applied to the randomized cohorts of both the feasibility and pivotal phases.

3.3 Suspension or Early Termination of the Clinical Investigation

While no formal statistical rule for early termination of the clinical investigation for either overwhelming or insufficient effectiveness of the device under investigation is defined, the Sponsor reserves the right to discontinue the clinical investigation at any stage or reduce the follow-up period with suitable written notice to the investigators. Possible reasons may include, but are not limited to:

- Unanticipated adverse device effect (e.g., UADE) occurs and it presents an unreasonable risk to the participating subjects
- Any oversight committee (e.g., Data Safety Monitoring Board) makes a recommendation to stop or terminate the clinical investigation (such as higher frequency of anticipated adverse device effects)
- Further product development is cancelled

Should the clinical investigation be discontinued by the Sponsor, subjects will be followed per routine hospital practice with device-related adverse events (AEs) reported to the Sponsor as per vigilance/commercial reporting requirements.

If the sponsor suspends or prematurely terminates the clinical investigation at an individual site in the interest of safety, the Sponsor will inform all other Principal Investigators.

Should the clinical investigation be terminated, the investigator shall return all clinical investigation materials (including devices) to the Sponsor, and provide a written statement as to why the premature termination has taken place to the Institutional Review Board (IRB) (if applicable). All applicable clinical investigation documents shall be subject to the same retention policy as detailed in **Section 11.5** of the CIP.

A Principal Investigator, IRB or regulatory authority may suspend or prematurely terminate participation in a clinical investigation at the investigational sites for which they are responsible. The investigators will notify the Sponsor and follow the requirements specified in the Clinical Investigation Agreement.

If suspension or premature termination occurs, the Sponsor will remain responsible for providing resources to fulfill the obligations from the CIP and existing agreements for following the subjects registered in the clinical investigation, and the Principal Investigator or authorized designee will promptly inform the registered subjects at his/her site, if appropriate.

4.0 ENDPOINTS

4.1 Primary Endpoint

The primary endpoint of the clinical investigation is a composite endpoint at 90 days, including the following components representing important safety and effectiveness endpoints:

- Cardiovascular Death
- Myocardial infarction (MI)
- Stroke
- Any unplanned repeat revascularization (PCI or CABG)
- Bleeding (BARC 3 or 5) up to 14 days post-device removal
- Severe hypotension, defined as: systolic blood pressure (SBP) or augmented diastolic pressure (whichever is greater) <90 mmHg while on device support requiring (1) more than one administration of OR (2) continuous infusion of inotropic/pressor medications to restore hemodynamics

- Change in aortic insufficiency from baseline to 90 days by echocardiographic assessment and defined as:

Baseline Assessment	90 Day Assessment
None	Moderate OR Severe
Trace	Moderate OR Severe
Mild	Moderate OR Severe

4.2 Descriptive Endpoints

A 2D bar chart consisting of 10 horizontal bars. The bars are solid black and are set against a white background. The heights of the bars increase progressively from left to right. The first bar is the shortest, and the tenth bar is the tallest, extending nearly to the top of the image. The bars are separated by small gaps.

4.3 Exploratory Endpoints

- Quality of Life questionnaires including EQ-5D-5L and Seattle Angina Questionnaire (SAQ) at baseline and 90 days

5.0 SUBJECT SELECTION AND WITHDRAWAL

5.1 Subject Population

This clinical investigation will enroll male and female subjects from the general interventional cardiology population. Subjects must meet all eligibility criteria and provide written informed consent prior to conducting any clinical investigation-specific procedures not considered standard of care.

5.2 Subject Screening and Informed Consent

5.2.1 Subject Screening

Assessment for general eligibility criteria is based on medical record review and interview with a candidate subject. Potential subjects presenting at the clinical sites will be fully informed about the clinical investigation. Subjects meeting general inclusion criteria and no exclusion criteria will be asked to sign an ICF if they wish to participate in the clinical investigation. Once a duly dated and signed ICF is obtained following the

established Informed Consent process as described in **Section 5.2.2**, the clinical investigation-specific, non-standard of care screening procedures may begin. Subjects must be screened for clinical investigation eligibility by a member of the site's clinical investigation team previously trained to the CIP.

In case the subject does not meet all inclusion criteria or meets any of the exclusion criteria, the subject is considered a screen failure. The Principal Investigator or the delegated clinical investigation personnel will record the screening failure in the hospital records and the electronic data capture (EDC) EDC as required.

5.2.2 Informed Consent

The Investigator or his/her authorized designee (if applicable) will conduct the Informed Consent process, as required by applicable regulations and the center's IRB. This process will include a verbal discussion with the subject on all aspects of the clinical investigation that are relevant to the subject's decision to participate, such as details of clinical investigation procedures, anticipated benefits, and potential risks of clinical investigation participation. Subjects must be informed about their right to withdraw from the clinical investigation at any time and for any reason without sanction, penalty or loss of benefits to which the subject is otherwise entitled. Withdrawal from the clinical investigation will not jeopardize their future medical care or relationship with the investigator.

During the discussion, the Principal Investigator or his/her authorized designee will avoid any improper influence on the subject and will respect subject's legal rights. Financial incentives will not be given to the subject. Subjects may be compensated for time and travel directly related to participating in the clinical investigation. The subject shall be provided with the ICF written in a language that is understandable to the subject and has been approved by the center's IRB. The subject shall have adequate time to review, ask questions and consider participation. The Principal Investigator or his/her authorized designee will make efforts to ensure that the subject understands the information provided. If the subject agrees to participate, the ICF must be signed and dated by the subject and thereafter by the person obtaining the consent prior to any clinical investigation-specific procedures. The signed original will be filed in the subject's hospital or research charts, and a copy will be provided to the subject. Once the subject signs the ICF, the subject is considered enrolled in the clinical investigation.

Failure to obtain informed consent from a subject prior to clinical investigation registration should be reported to Sponsor within 5 working days and to the reviewing center's IRB according to the IRB's reporting requirements. Revisions to the informed consent will be approved by the Sponsor and the IRB prior to re-consenting subjects.

If during the clinical investigation, new information becomes available that can significantly affect a subject's future health and medical care, the Principal Investigator or his/her authorized designee will provide this information to the subject. If relevant, the subject will be asked to confirm their continuing informed consent in writing.

In addition, an authorization for use and disclosure of the subject's protected health information, in accordance with the Health Insurance Portability and Accountability Act (HIPAA), must be obtained from the subject or their legally authorized representative in applicable geographies.

For live cases at congresses, the subjects need to sign a specific Live Case ICF, approved by the IRB and by the Sponsor, as well as by the competent authorities (e.g., FDA), as applicable. The investigator must request Sponsor approval prior to performing a Live Case.

Vulnerable Populations

No vulnerable populations will be recruited for this clinical investigation. Vulnerable patients are defined as patients whose willingness to volunteer in a clinical investigation could be unduly influenced by the expectation, whether justified or not, of benefits associated with participation or of retaliatory response from senior members of a hierarchy in case of refusal to participate. Incapacitated individuals, defined as persons who are mentally ill, mentally handicapped, or individuals without legal authority, are excluded from the study population. Additionally, pregnant women are excluded from the study population.

Individuals unable to read or write may be enrolled in this clinical investigation. Informed consent will be obtained through a supervised oral process. An independent witness will be present throughout the Informed Consent process. The written ICF and any other information will be read aloud and explained to the prospective subject and he/she will sign and personally date the ICF. The witness will also sign and personally date the ICF attesting that the information was accurately explained, and that informed consent was freely given.

5.3 Eligibility Criteria

Subjects must meet all of the inclusion criteria to be considered for the clinical investigation. If any of the exclusion criteria are met, the subject is excluded from the clinical investigation and cannot be registered. Assessment for general eligibility criteria is based on medical records of the site and interview with a candidate subject. If some of the clinical and laboratory tests are not included in site standard tests, they must be done but after written informed consent is obtained.

5.3.1 Inclusion Criteria

5.3.1.1 General Inclusion Criteria:

1. At least 18 years of age

2. Subject is undergoing elective or urgent high-risk PCI procedure and is hemodynamically stable.
3. Subject is indicated for a revascularization of at least one *de novo* or restenotic lesion in a native coronary vessel or bypass graft.
4. A heart team, including a cardiac surgeon, has determined high-risk PCI is an acceptable therapeutic option.
5. Subject must provide written informed consent prior to any clinical investigation related procedure.

5.3.1.2 Imaging Inclusion Criteria:

1. The presence of complex coronary artery disease (CAD) makes hemodynamic instability resulting from repeat episodes of reversible myocardial ischemia during PCI likely. Complex CAD is defined as an ejection fraction of <50% by echocardiographic assessment AND at least one of the following:
 - a. Intervention of the last patent coronary conduit, OR
 - b. Intervention of an unprotected left main artery, OR
 - c. Intervention on patient presenting with triple vessel disease defined as at least one significant stenosis (at least 50% diameter stenosis on visual assessment) in all three major epicardial territories

5.3.2 Exclusion Criteria

5.3.2.1 General Exclusion Criteria:

1. Emergency PCI
2. Any prior coronary revascularization within the last 6 months
3. Any MI with elevated cardiac biomarker (creatinine kinase-MB (CK-MB) or troponin >1X upper limit of normal (ULN)) and no evidence of at least 1 consecutive CK-MB or troponin value trending downward from previous value (at least 4 hours apart) OR ST Elevation MI (STEMI) within 72 hours prior to the index procedure regardless of the level of cardiac biomarker
4. Cardiac arrest within 24 hours of procedure requiring cardiopulmonary resuscitation (CPR) or defibrillation
5. Any use of a mechanical circulatory support device within 14 days prior to the index procedure (Note: Subjects must be hemodynamically stable without any hemodynamic support to be eligible for this clinical investigation.)
6. Hemodynamic support with a mechanical circulatory support device (e.g., the HeartMate PHP, Impella, intra-aortic balloon pump (IABP) or extracorporeal membrane oxygenation (ECMO)), post-PCI is anticipated.

7. Any condition that requires discontinuation of antiplatelet and/or anticoagulant therapy within 90 days following the index procedure (e.g., planned noncardiac surgery).
8. Any use of vasopressors or inotropes within 24 hours prior to the index procedure
9. Staged PCI is planned within 90 days following device removal.
10. Cardiogenic shock (SBP <90 mmHg for >1 hour with either cool clammy skin OR oliguria OR altered sensorium AND cardiac index <2.2 L/min/m²)
11. History of aortic valve replacement or repair
12. Severe peripheral vascular disease that will preclude the use of a 14F access sheath, which is required for the insertion of the HeartMate PHP catheter (If the investigator is unsure of the presence or severity of the peripheral vascular diseases for study device access, an appropriate imaging assessment (e.g., duplex ultrasound, angiogram or computerized tomography) should be performed to verify the access before randomization.)
13. Known abnormalities of the aorta that would preclude surgery, including aneurysms and significant tortuosity or calcifications
14. Subject is on hemodialysis.
15. Liver dysfunction with elevation of liver enzymes and bilirubin levels to $\geq 3X$ ULN or Internationalized Normalized Ratio (INR) ≥ 1.6 or lactate dehydrogenase (LDH) $> 2.5X$ ULN
16. Abnormal coagulation parameters (platelet count $\leq 75000/\text{mm}^3$ or INR ≥ 1.6 or fibrinogen $\leq 1.5 \text{ g/l}$)
17. Active systemic infection requiring treatment with antibiotics
18. Subject had active COVID-19 symptoms and/or a positive test result within the prior 2 months.
19. Stroke or transient ischemic attack (TIA) within 6 months of procedure
20. Any allergy or intolerance to ionic and nonionic contrast media, anticoagulants (including heparin), or antiplatelet therapy drugs that cannot be adequately premedicated
21. Subject is pregnant (For a female subject of childbearing potential, a pregnancy test must be performed within 14 days (≤ 14 days) prior to the index procedure per site standard test).
22. Participation in another clinical study of an investigational drug or device that has not met its primary endpoint
23. Presence of other anatomic or comorbid conditions, or other medical, social, or psychological conditions that, in the investigator's opinion, could limit the subject's

ability to participate in the clinical investigation or to comply with follow-up requirements, or impact the scientific soundness of the clinical investigation results

24. Life expectancy <1 year

5.3.2.2 Imaging Exclusion Criteria:

1. Mural thrombus in the left ventricle
2. Documented presence of aortic stenosis (orifice area of 1.5cm² or less)
3. Moderate to severe aortic insufficiency by echocardiographic assessment

5.4 Subject Registration

Registration is the point when the subjects enter the clinical investigation, and registration for the roll-in and the randomized cohorts in the clinical investigation will be defined differently as described below.

A. Roll-in Cohort

Subjects in the roll-in cohort will not be randomized. A roll-in subject will be considered registered only after signing an ICF, meeting all eligibility requirements, and after a HeartMate PHP device is inserted.

Roll-in screen failures are further defined as:

1. Roll-in subjects who sign consent and subsequently fail any inclusion or exclusion criteria. No follow-up is required.
2. Roll-in subjects who sign consent and meet initial inclusion and exclusion criteria but who subsequently do not undergo device insertion due to previously undiagnosed anatomic abnormalities (e.g., peripheral vascular disease) which preclude device insertion or unforeseen clinical conditions that preclude device insertion. No follow-up is required.

B. Randomized Cohort

Subjects in the randomized cohort will be randomized only after the subjects have signed the ICF and met all eligibility requirements. Randomization assignments will be given through the EDC Study Site Portal. Subjects will be considered registered in the clinical investigation once randomized and must follow all CIP requirements. Randomized subjects who do not undergo device placement due to previously undiagnosed anatomic abnormalities (e.g. peripheral vascular disease) which precludes device placement, will still be considered registered and must follow all CIP requirements. Once a subject is randomized, PCI should be performed as soon as possible.

5.4.1 Medicare Beneficiaries

This clinical investigation will recruit Medicare beneficiaries and therefore conforms to all standards of Medicare coverage requirements. The Risks and Benefits section describes how all registered subjects, including Medicare beneficiaries, may be affected by the device under investigation.

A portion of the subjects registered in the clinical investigation display characteristics consistent with the Medicare population based on age. The clinical investigation results will be analyzed by age (<65 years and \geq 65 years) and compared to ensure that the outcomes are similar between the Medicare and non-Medicare populations.

5.4.2 Historically Under-Represented Demographic Subgroups

The Sponsor intends to implement FDA's guidance on sex-specific data in medical device clinical investigations to ensure adequate representation of women and other traditionally under-represented demographic subgroups in this clinical investigation. As noted in the guidance, some barriers to participation of women and ethnic minorities in clinical investigations have traditionally been:

- Lack of understanding about main obstacles to participation of such subgroups in clinical research
- Inclusion/exclusion criteria potentially not needed to define the clinical investigation population may unintentionally exclude specific subgroups
- Under diagnosis of disease etiologies and pathophysiology leading to under referral of demographic subgroups
- Avoidance of specific subgroups by investigators and Sponsors due to the perception that it takes more time and resources to recruit them
- Fear of fetal consequences (for female participants)
- Family responsibilities limiting women's ability to commit time for follow-up requirements

The Sponsor will take the following steps to ensure adequate representation of women and racial or ethnic minorities in this clinical investigation:

- The Sponsor will provide training to investigational site personnel to ensure adequate representation of these demographic subgroups
- The Sponsor will approach sites without bias or consideration for specific demographic subgroups

5.5 Subject Discontinuation

Each registered subject shall remain in the clinical investigation until completion of the required 90-day (\pm 30 days) follow-up visit however, a subject's participation in any clinical investigation is voluntary and the subject has the right to withdraw at any time

without penalty or loss of benefits. Conceivable reasons for discontinuation may include, but not be limited to, the following:

- Subject death
- Subject voluntary withdrawal
- Subject withdrawn by the Investigator
- Subject lost-to follow-up as described below
- Subject's follow-up is terminated according to **Section 3.3**.

The Sponsor must be notified of the reason(s) for subject discontinuation. The site will provide this information to the Sponsor. Investigators must also report this to their respective IRB as defined by their institution's procedure(s).

No additional follow-up will be required or data recorded from subjects once discontinued from the clinical investigation, except for the status (deceased/alive).

In case of subject withdrawal of consent, the site should make attempts to schedule the subject for a final clinical investigation visit prior to withdrawal. At this final follow-up visit, the subject will undergo the following assessments:

- Clinical assessment
- Echocardiographic assessment

Lost-to-Follow-up

There will be only one scheduled follow-up visit at 90 days (± 30 days) in this clinical investigation. If the subject misses the scheduled 90-day follow-up visit and the attempts at contacting the subject detailed below are unsuccessful, then the subject is considered lost-to-follow-up. Site personnel shall make all reasonable efforts to locate and communicate with the subject (and document these efforts in the source documents), including the following:

- A minimum of two telephone calls on different days over the specified follow-up window to contact the subject should be recorded in the source documentation, including date, time and initials of site personnel trying to make contact.
- If these attempts are unsuccessful, a letter (certified, if applicable) should be sent to the subject.

Note: Telephone contact with general practitioner, non-clinical investigation cardiologist or relative without the presence of the subject or indirect documentation obtained via discharge letters will not be considered as subject contact.

5.7 **Expected Duration of Each Subject's Participation**

The expected duration of each subject's participation in the clinical investigation is 90 days following the removal of the study device.

5.8 **Number of Subjects**

In the feasibility phase of the clinical investigation, 195 subjects, including 75 HeartMate PHP roll-in and 120 randomized subjects, were registered.

In the pivotal phase of the clinical investigation, up to 480 HeartMate PHP roll-in subjects and a minimum of 473 and a maximum of 716 randomized subjects will be registered.

5.9 **Estimated Time Needed to Register the Required Number of Subjects**

The time needed to register the required number of subjects for the pivotal phase of this clinical investigation is estimated to be up to 39 months.

6.0 **TREATMENT AND EVALUATION OF ENDPOINTS**

In this clinical investigation, data will be collected at baseline, during the index procedure, post-procedure, at discharge, and at 90 days post-device removal to assess subject eligibility as well as to evaluate the safety and effectiveness of the study devices. The clinical investigation-required assessments and the timing of data collection for each assessment will be described below. A complete listing of the clinical investigation-required assessments and schedule can be found in **Table 2: Clinical Investigation Assessment Schedule in Section 6.9**.

6.1 **Baseline Assessments**

The following data will be collected at baseline to assess the subjects' eligibility to participate in this clinical investigation or for baseline reference.

- Subject demographics
- Subject medical history
- COVID-19 Assessment: If the patient had a COVID-19 test at any point before enrollment in the study, details of the test, date conducted, and outcome should be captured in the COVID-19 Assessment Log Form.
- Physical examination/Vital signs

- Laboratory tests except for cardiac biomarkers (within 14 days prior to the index procedure; refer to **Table 2** for required baseline laboratory tests)
- Cardiac biomarkers: CK-MB and troponin (NO high-sensitivity troponin) are both required within 48 hours prior to the index procedure.
- 12-lead electrocardiogram (ECG) (within 48 hours prior to the index procedure)
- Echocardiogram (within 60 days prior to the index procedure). Images need to be uploaded to the Echocardiographic Core Laboratory via Bioclinica website. For a baseline echocardiogram performed prior to the subject signing informed consent, the investigators will need to assess whether the available baseline echocardiogram captures the appropriate images of aortic valve required for a quantitative assessment of aortic regurgitation by the Echocardiographic Core Laboratory per the Echocardiographic Core Laboratory guidance. If not, a baseline echocardiogram will need to be repeated per the Echocardiographic Core Laboratory guidance before the index procedure.
- Diagnostic angiogram (within 60 days prior to the index procedure). Images need to be uploaded to the Angiographic Core Laboratory via Bioclinica website along with the information on the size of the diagnostic catheter to obtain the SYNTAX score.
- Health assessments (Euroscore II, Society of Thoracic Surgery (STS) mortality score and New York Heart Association (NYHA) heart failure class) (within 30 days prior to the index procedure)
- Quality of life questionnaires (SAQ and EQ-5D-5L) (within 30 days prior to the index procedure)
- Concomitant use of anticoagulant and antiplatelet medications

For physical examination, vital signs, laboratory tests and echocardiogram, refer to **Section 6.8** for further details.

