1.3 Clinical Investigation Design

SHIELD II is a prospective, randomized, open-label, multi-center clinical investigation that will register subjects at up to 120 sites in the U.S. Subjects in this clinical investigation will be randomly assigned to the HeartMate PHP or Impella in a 2:1 ratio. The primary endpoint is a composite endpoint at 90 days, including cardiovascular death, myocardial infarction (MI), stroke, unplanned repeat revascularization, bleeding of BARC 3 or 5 up to 14 days post-device removal, severe hypotension and change in aortic insufficiency from baseline to 90 days by echocardiographic assessment. HeartMate PHP will be tested for non-inferiority in the primary endpoint compared to Impella. Any Impella device approved for use in high-risk PCI can be used as the control device. All registered subjects will be followed for 90 days. This clinical investigation is conducted to support the pre-market approval of the HeartMate PHP for the indication of high-risk PCI.

The SHIELD II clinical investigation is divided into two phases chronologically: a feasibility phase, which includes subjects registered under the CIP versions 2-4[†] prior to January 30, 2017, and a pivotal phase, which includes subjects to be registered under version F or a later version of the CIP. Both phases consist of a non-randomized roll-in cohort and a randomized cohort. The roll-in cohort is designed to prevent a learning curve from biasing the clinical investigation results.

There were 195 subjects, including 75 HeartMate PHP roll-in and 120 randomized subjects, registered at 48 U.S. sites in SHIELD II prior to January 30, 2017, and these subjects are now considered in the feasibility phase of the clinical investigation. All registered subjects in the

[†] Previous versions of the SHIELD II CIP in the feasibility phase were designated numerically from version 1 to version 5 (no subjects were registered under versions 1 and 5 of the CIP). Starting from the pivotal phase, the CIP is designated alphabetically and starts as version F.

Statistical Analysis Plan

feasibility phase were already beyond the time point of the 90-day follow-up visit, and the feasibility phase of the clinical investigation reached its end in 2017.

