2.2.2 Descriptive Statistics for Categorical Variables

For binary variables (e.g. gender, diabetic status, etc.), results within treatment arm will be summarized with subject counts and percentages/rates, and where applicable, with exact 95% Clopper-Pearson¹ confidence intervals.

For events of interest, relative risks (i.e., the ratio of rates), confidence interval for the relative risks, the difference in rates and the confidence interval for difference in rates, and p-values may also be presented for hypothesis generating purposes.

For the determination of event rates, the denominators are defined as below based on the type of events.

- Primary endpoint event and its components

The denominator of the primary endpoint event rate will exclude subjects in the analysis population who terminated from the study [REDACTED] without a primary endpoint event or any subject who completes the 90-day follow-up without aortic insufficiency data at either baseline or 90-day follow-up and without a primary endpoint event. The same denominator rule will apply to individual component of the primary endpoint except for change in aortic insufficiency, which is an imaging endpoint and will follow the denominator rule set forth for missing data handling.

Statistical Analysis Plan

- Site-reported Adverse Events, Adverse Device Effects and Adverse Event related Descriptive Endpoints

[REDACTED]

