2.3 Endpoint Analysis

2.3.1 Primary Endpoint(s)

The primary endpoint, a composite of safety and effectiveness at 90 days, will be evaluated using the difference in event rates in the ITT population of the pivotal phase. The hypothesis test is designed to show non-inferiority of HeartMate PHP to Impella for the primary endpoint with one-sided alpha of 0.025.

[REDACTED]

ICER

[REDACTED]

If non-inferiority is met, superiority testing will be performed with a two-sided alpha of 0.05.

[REDACTED]

[REDACTED]

The data will be analyzed for superiority using Fisher's exact test.

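### Protocol 5.5 stops recording everything except vital status after any discontinuation, not only after withdrawal of consent, so later events and cause of death are not collected for the ITT composite

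*Protocol*

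**What the plan says.** Protocol 5.5 gives a non-exhaustive list of reasons for discontinuation. Besides death and voluntary withdrawal it names "Subject withdrawn by the Investigator" and "Subject lost-to follow-up as described below". One sentence then governs what happens next, whatever the reason: "No additional follow-up will be required or data recorded from subjects once discontinued from the clinical investigation, except for the status (deceased/alive".

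A closing visit, clinical and echocardiographic, is described for one reason only: "In case of subject withdrawal of consent, the site should make attempts to schedule the subject for a final clinical investigation visit prior to withdrawal". Under the loss-to-follow-up heading, a note says that speaking to a relative or another physician does not count as contact, and that "indirect documentation obtained via discharge letters will not be considered as subject contact". Protocol 7.3.1 ends safety reporting when a subject withdraws or concludes participation.

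On the analysis side, SAP 1.3 states: "The primary endpoint is a composite endpoint at 90 days, including cardiovascular death, myocardial infarction (MI), stroke, unplanned repeat revascularization", together with bleeding, severe hypotension and change in aortic insufficiency. According to SAP 2.3.1 this endpoint "will be evaluated using the difference in event rates in the ITT population of the pivotal phase". SAP 2.2.2 says: "The denominator of the primary endpoint event rate will exclude subjects in the analysis population who terminated from the study"; after a redacted qualifier, the sentence limits this to those without a primary endpoint event. SAP 2.9 uses available data with missing data excluded.

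**The concern.** An intention-to-treat comparison at 90 days needs each randomized subject's outcome to 90 days. Protocol 3.1 shares that aim, since it asks that all registered subjects be followed until 90 days after device removal. Section 5.5 works against it. It does not distinguish a subject who refuses further data collection from one who has stopped for another reason and whose records could still be used with consent.

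Vital status cannot fill the gap. The composite counts cardiovascular death only, and deceased/alive gives neither the cause of death nor any MI, stroke or revascularization. Under SAP 2.2.2 the uncollected outcome can then become an exclusion from the denominator.

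The loss need not be random. Protocol 3.2.1 confirms that investigators know the assignment, and 5.5 sets no criteria for withdrawal by the investigator. Such withdrawal can therefore depend on both arm and prognosis. The bias could run in either direction; the direction that matters for a non-inferiority claim is more unseen events in the HeartMate PHP arm.

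**Working it through.** **1. Which subjects and events the rule reaches**

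- *Withdrawn by the investigator:* the subject may leave at any time before day 90. From then on only vital status is recorded, and no closing visit is described. This is the clearest gap.
- *Lost to follow-up:* this is declared only after the 90-day visit (window 90 ± 30 days, so days 60 to 120) is missed and contact attempts fail. Until then 7.3.1 requires all adverse events to be documented, and 6.7 asks for every effort to obtain information on events treated at other hospitals. The gap is an event first learned of after the subject is declared lost: the no-data sentence in 5.5 covers it, while 6.7 points the other way.
- *Event before discontinuation:* kept. SAP 2.2.2 excludes terminated subjects only if they have no primary endpoint event.

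**2. The plan's own sample size**

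Visible inputs (SAP 2.3.1 and 2.4): control rate 20%, margin 10%, one-sided alpha 0.025, 2:1 allocation, 315 + 158 = 473. The HeartMate PHP rate, power and attrition are not visible.

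With equal 20% rates and 80% power, the control arm needs (1.960 + 0.842)² × (0.16/2 + 0.16) / 0.10² = 188.4, rounded up to 189, or 567 in total. At 85% and 90% power the totals are 648 and 759. None of these is 473. Solving backwards, 315/158 gives 80, 85 or 90% power if the HeartMate PHP rate is about 19.1, 18.4 or 17.6% with no attrition. The figure of 473 therefore cannot be checked from the visible text and is not shown to be wrong. This point does not depend on it.

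**3. Bias in the tested difference (assumed inputs)**

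Let d be the non-evaluable share per arm, p = 20% the rate in retained subjects of both arms, and q the unseen rate in the non-evaluable. The true rate in an arm is (1 − d)p + dq, while the available-data rate is p. With equal d and p in the two arms, the available-data difference falls short of the true difference by d × (q_PHP − q_Impella).

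| d per arm | q PHP | q Impella | Understatement of the difference |
|---|---|---|---|
| 5% | 40% | 20% | 0.05 × 0.20 = 1 point |
| 10% | 40% | 20% | 0.10 × 0.20 = 2 points |
| 5% or 10% | 40% | 40% | 0 |

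**4. Room before non-inferiority fails**

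The test statistic is not visible, so an unpooled Wald limit is assumed. Find the observed excess x at which

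x + 1.96 × √[(0.20 + x)(0.80 − x)/315 + 0.20 × 0.80/158] = 0.10.

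At x = 0.0225 the root is √(0.000549 + 0.001013) = 0.0395, and 0.0225 + 1.96 × 0.0395 = 0.100. The result still passes at an observed excess of up to about 2.3 points. That figure uses all 315 and 158 subjects; losses make it smaller.

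**5. Precision when losses are balanced**

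Power = Φ(0.10/SE − 1.96) if both true rates are 20%. With 315/158, SE = √(0.16/315 + 0.16/158) = 0.0390 and power is 72.7%. With 5% or 10% non-evaluable in each arm it is 70.5% or 68.2%.

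**The case against.** Much of the plan limits the damage. While a subject is on study, deaths and other adverse events are reportable, 6.7 asks for outside records, 6.8 asks for billing data from rehospitalizations elsewhere, and 6.6 keeps the 90-day form for hospitalized subjects and allows home visits. Severe hypotension occurs on device support and the bleeding component closes at 14 days, so both are mostly captured before anyone discontinues. SAP 2.12 plans worst-case, tipping-point and multiple-imputation analyses of the primary endpoint. All of this stands. The sensitivity analyses probe the missing data but cannot supply them, and their details are redacted.

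Three stronger readings are tempting, and the documents do not support them.

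- *Discharge letters may not be used.* The note only defines subject contact. It does not bar such letters as source documents.
- *A death after discontinuation can never be classed as cardiovascular.* A rule for deaths of unknown cause may sit in the redacted text or in the CEC charter, which is not supplied. Such a rule could assign a class but would not provide the missing facts. Only the gap in collection can be asserted.
- *The plan throws away recorded events, or the shift in one arm's rate is the bias.* Events before discontinuation are kept. A one-arm shift is not the error in the tested difference, because equal losses with equal unseen rates cancel.

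The size is also open to challenge. Because two components accrue early, 40% is a demanding assumption for later events. The 5-10% also includes withdrawals of consent and missing echocardiograms, which the fix would not recover.

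**Conclusion.** The point holds in a limited form. Section 5.5 does not separate withdrawal of consent from other discontinuation, so endpoint events and cause of death arising afterwards are not collected, although the ITT composite needs them. The case is strongest for withdrawal by the unblinded investigator. For loss to follow-up it reduces to reconciling 5.5 with 6.7.

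Under the assumed inputs the understatement is 1-2 points against about 2.3 points of room, so it could decide a close result. It would not matter if losses and unseen event rates were equal in the two arms, beyond some loss of precision. No visible text says how many subjects will be discontinued or why, so these figures illustrate scale and do not predict bias. This is an inexpensive improvement worth making, and not evidence that the primary analysis is invalid.

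**What to change.** In Protocol 5.5, confine the no-data rule to subjects who withdraw consent to data collection. For every other discontinued subject:

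- collect death with its cause, MI, stroke, revascularization, and BARC 3 or 5 bleeding within its 14-day limit, through day 90, from medical records, treating physicians, relatives or public records;
- submit these events to the CEC and include them in the ITT analysis;
- state that these sources do not replace the 90-day echocardiogram for aortic insufficiency.

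Align 7.3.1 and the consent form, and reconcile 5.5 with 6.7 for events learned of after a subject is declared lost. SAP 2.2.2 should also say how a discontinued subject with complete records and no event is counted; if only those with an event return to the denominator, the rate is pushed upwards.

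The cost is protocol and consent wording plus record requests for what should be a small share of subjects, with no added visits. Chart-derived events may be less complete than visit data.
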